## 5.5. Extent of Study Treatment Exposure and Compliance

### 5.5.1. Measurement of Compliance

The compliance with protocol-defined study drug administration will be calculated as follows:

Treatment Compliance= (Number of study drug injections during exposure period) / (Number of planned study drug injections during exposure period) x 100%

The summary of study drug administration will include the number of study drug doses administered and treatment compliance. The treatment compliance will be presented by the following specific ranges for each treatment group: <80%, and ≥80%.

### 5.5.2. Exposure to Study Drug and Observation Period

The duration of treatment (Q4W dosing) exposure during the study in day is calculated as:

(Date of last study drug injection – date of first study drug injection) + 28 days

The calculations do not take into account temporary dosing interruption including due to COVID-19. The summary of exposure to study drug will include the number of study drug doses administered and the duration of exposure. Duration of exposure will be summarized for each treatment group using the number of patients, mean, SD, minimum, median, Q1, Q3, and maximum.

In addition, the duration of exposure will be summarized categorically by counts and percentages for each of the following categories cumulatively by these categories: ≥ 28 days, ≥ 56 days, ≥ 84 days, and ≥ 112 days with an increment of 4 weeks for each subsequent category.

The duration of observation period during the study in days is calculated as:

(Date of the last visit – date of the first study drug injection) +1.

The duration of observation period will be summarized descriptively using number of patients, mean, SD, median, Q1, Q3, minimum and maximum. In addition, the number (%) of subjects with observation periods will be presented by specific time periods. The time periods of interest are specified as:

< 8 days, ≥ 8 days, ≥ 15 days, ≥ 22 days, ≥ 29 days, ≥ 57 days, ≥ 85 days, ≥113 days, ≥141 days, ≥169 days, and ≥197 days.

## 5.6. Analyses of Efficacy Variables

The analyses of efficacy variables are described in the subsections below and summarized in [Appendix 2](#). The intercurrent events, strategies, and the corresponding missing data handling approaches for the estimands of interest for the co-primary endpoints (**only in European Union [EU] and EU Reference Market Countries**) and key secondary endpoints are provided below.

Endpoint Category	Estimands			
	Endpoints	Population	Intercurrent event(s) handling strategy and missing data handling	Population-level summary/Analysis Method
Co-primary (Proportion)	
 
Proportion of patients with IGA 0 or 1 (on a 5-point scale) at week 16
 
Proportion of patients with EASI-75 at week 16
 
	FAS	
The intercurrent events will be handled as follows:
 
 
Discontinuation of study intervention: Data collected after the patient discontinued treatment will be included in the analyses (treatment policy strategy).
 
Initiation of rescue treatment: Patients will be considered as non-responders after such events (composite strategy).
 
 
Missing data imputation rules:
 
 
Missing data due to withdrawn consent, AE, LOE will be imputed as non-responder.
 
Missing data due to any other reason including COVID-19 will be imputed using multiple imputation (MI)
 
	
Proportion of response/                      CMH test adjusted by randomization strata

Estimands				
Endpoint Category	Endpoints	Population	Intercurrent event(s) handling strategy and missing data handling	Population-level summary/Analysis Method
Key Secondary (Continuous)	
 
Percent change in EASI score from baseline to week 16
 
Percent change from baseline to week 16 in weekly average of daily worst scratch/itch NRS score
 
	FAS	
The intercurrent events will be handled as follows:
 
 
Discontinuation of study intervention: Data collected after the patient discontinued treatment will be included in the analyses (treatment policy strategy).
 
Initiation of rescue treatment: data after rescue treatment will be assigned by postbaseline worst-observation- carried-forward (WOCF) (hypothetical strategy). If there is no post-baseline assessment, the baseline value will be used (hypothetical strategy).
 
 
Missing data imputation rules:
 
 
Missing data due to withdrawn consent, AE, or lack of efficacy will be imputed by postbaseline WOCF. If there is no post-baseline assessment,
 
	Mean Change from baseline/ ANCOVA model with treatment and randomization strata as covariates

		Estimands		
Endpoint Category	Endpoints	Population	Intercurrent event(s) handling strategy and missing data handling	Population-level summary/Analysis Method
			the baseline value will be used. 
 
Missing values due to other reasons including COVID-19 will be imputed by MI approach
 
	

### 5.6.1. Analysis of Primary/Co-Primary Efficacy Variable

The Cochran-Mantel-Haenszel (CMH) test adjusted by randomization strata (baseline weight group:  $\geq 5$ - $<15$  kg and  $\geq 15$ - $<30$  kg), baseline disease severity (IGA=3 and 4), and region/country (North America, Europe)) will be used for the analysis of percentage of patients with IGA 0 or 1 at week 16. Similar procedures will be used for percentage of patients with EASI-75 at week 16. At the time of this SAP, all patients for this study have been randomized. The smallest stratum (region = EU, baseline weight  $<15$  kg, IGA=3) has 2 subjects only. All other strata have more than 10 patients. In all statistical analysis utilizing stratification factors in CMH test, stratum (region = EU, baseline weight  $<15$  kg, IGA=3) will be combined with the stratum (region = EU, baseline weight  $\geq 15$  kg, IGA=3).

#### Handling of dropouts or adjudicated rescue treatment or missing value for the binary response variables as the primary analysis:

- If a patient withdraws consent from the study or discontinues due to AE or lack of efficacy (LOE), this patient will be counted as a non-responder for the time points after withdrawal.
- To account for the impact of rescue treatment on the efficacy effect: if rescue treatment is used (see Section 4.3, Appendix 1, and Appendix 6 for rescue treatment), the patient will be specified as a non-responder from the time the rescue treatment is used.
- If the patient has the missing value at week 16 due to any other reasons including COVID-19, the data will be imputed using multiple imputation (MI) based on all observed values as described below:
- The underlying continuous (e.g. EASI) or categorical variable (e.g. IGA) will be imputed 40 times to generate 40 complete data sets by using the SAS procedure MI using the following steps.
  - **Step 1:** The monotone missing pattern is induced by Markov Chain Monte Carlo (MCMC) method in MI procedure using seed number 12345. The monotone missing pattern means that if a patient has missing value for a variable at a visit, then the values at all subsequent visits for the same variable are all missing for the patient.

- **Step 2:** The missing data at subsequent visits will be imputed using the regression method for the monotone pattern with seed number 54321 and adjustment for covariates including treatment groups, randomization strata (baseline weight group, baseline IGA and region), and relevant baseline variables. For the categorical variable, such as IGA, a logistic regression under monotone option will be used.

Based on each imputed data, the response status (responder or non-responder) will be determined for each subject.

Once imputations are made, the week 16 data (binary response) of each of the 40 complete datasets will be analyzed using CMH test. The SAS MIANALYZE procedure will be used to generate valid statistical inferences by combining results from the 40 analyses using Rubin's formula. An appropriate transformation (such as Wilson-Hilferty transformation) of CMH test statistics can be used in Rubin's formula (Ratitch et. al 2013).

### **Sensitivity analyses:**

Sensitivity analysis on primary and co-primary efficacy endpoints will be performed using the Tipping-point analysis method.

To assess the robustness of primary analysis results, a delta-adjusting pattern-mixture approach for tipping point analysis (2013, Ratitch) under MNAR (missing not at random) assumption, will be conducted for the co-primary endpoints. The impact from missing data on the comparisons in proportion of patients achieving IGA 0/1 (co-primary endpoint: EASI-75, **only in European Union [EU] and EU Reference Market Countries**) at week 16 between dupilumab and placebo control group will be examined as follows.

- A sequence of analyses will be performed with the adjustment to artificially decrease the response rate in dupilumab group and increase the response rate in placebo group with a fixed and definite set of values for data imputation.
- For each combination of increasing response rate in placebo and decreasing response rate in dupilumab, multiple imputed datasets will be generated and analyzed using CMH test. The results obtained from multiple imputed datasets will be combined to generate statistical inference, i.e. p-value and treatment difference between 2 treatment groups.
- A “tipping point” will be identified while the result is no longer statistically significant (i.e. p-value >0.05).

### **5.6.2. Analyses of Secondary Efficacy Variables**

All secondary endpoints will be evaluated based on the FAS population.

The binary secondary efficacy endpoints will be analyzed using the same approaches used for the analysis of the primary endpoints as described in Section 5.6.1.

The continuous endpoints (e.g. EASI, worst scratch/itch NRS score) will be analyzed using analysis of covariance (ANCOVA) model with treatment, randomization strata (baseline weight group:  $\geq 5$ -<15 kg and  $\geq 15$ -<30 kg), baseline disease severity (IGA=3 and 4), region/country (North America, Europe) and relevant baseline value included in the model as the primary analysis method. The missing data for continuous endpoints will be imputed by the pattern-mixture

approach (MI-WOCF Method). The WOCF approach will be used for data after rescue or missing due to withdrawn consent, AE, and lack of efficacy. To be specific, the missing data will be imputed by postbaseline worst-observation-carried-forward (WOCF) if there is at least one non-missing postbaseline value or by baseline value if there is no postbaseline value. The multiple imputation (MI) approach will be used for the missing due to other reasons, including reasons due to COVID-19. The MI will be performed based on all observed data before the imputation by WOCF approach. To account for the uncertainty in the imputation, missing data from the FAS will be imputed 40 times to generate 40 complete data sets by using the SAS procedure MI following the 2 steps below:

**Step 1:** The monotone missing pattern is induced by Markov Chain Monte Carlo (MCMC) method in MI procedure using seed number 12345. The monotone missing pattern means that if a patient has missing value for a variable at a visit, then the values at all subsequent visits for the same variable are all missing for the patient.

**Step 2:** The missing data at subsequent visits will be imputed using the regression method for the monotone pattern with seed number 54321 and adjustment for covariates including treatment groups, randomization strata (baseline weight group, baseline IGA and region), and relevant baseline.

Once imputations are made, the week 16 data of each of the 40 complete datasets will be analyzed using ANCOVA model with treatment, randomization strata (baseline weight group, baseline IGA and region), and relevant baseline included in the model, and the SAS MIANALYZE procedure will be used to generate valid statistical inferences by combining results from the 40 analyses using [Rubin's](#) formula.

The imputation model will include:

- The covariates included in the ANCOVA model, including the treatment group, the baseline value and the randomization strata (baseline weight group, baseline IGA and region)
- Measured endpoint values at every clinic visit (e.g. week 1, 2, 4, 8, 12 and week 16 for EASI)

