9.5.2.2. Secondary Efficacy Analysis

For binary endpoints, the secondary efficacy analysis will use the same approach as that used for the primary efficacy analysis.

For continuous endpoints, an analysis of covariance (ANCOVA) model will be used for the FAS with treatment group, randomization stratification factors (region/country, baseline disease severity, and baseline weight group) and relevant baseline measurement included in the model.

Similarly, to account for the impact of rescue treatment on the efficacy effect, patients' efficacy data through week 16 after the rescue treatment use will be set to missing. The missing data for continuous endpoints will be imputed by the pattern-mixture approach where the WOCF approach will be used for the missing due to rescue treatment, AE, and lack of efficacy and the multiple imputation (MI) approach will be used for the missing due to other reasons. The MI Statistical Analysis Software (SAS) procedure with Markov Monte Carlo algorithm will be applied for multiple times. The complete datasets created based on the pattern-mixture approach will be analyzed using the ANCOVA model defined previously, and the SAS MIANALYZE procedure will be used to generate valid statistical inferences by combining results from these multiple analyses using Rubin's formula (Rubin, 1987).

All efficacy data will be used for analysis regardless of whether the patient is on study treatment or discontinues the study treatment but remains in the study. In addition, the MI with the ANCOVA model and the ANCOVA model based on LOCF or WOCF imputation method will be performed as the sensitivity analyses. Additional details on sensitivity analyses will be provided in the SAP.

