- EASI-75 at week 16
- improvement (reduction) of weekly average of worst scratch/itch scale  $\geq 4$  from baseline to week 16

All above analyses will be performed on the FAS for

- All observed data, regardless if rescue treatment is used or data is collected after study drug withdrawal
- All observed data with censoring after rescue treatment use

The proportion of patients for whom biomarker concentrations “normalize” (shift from above normal to within the normal range) at Week 16 will also be evaluated.

The additional analysis will be performed on the following biomarkers at week 16:

- Serum total IgE
- Serum LDH

Serum total IgE and LDH have established clinical assays; the upper limit of normal (ULN) from the central lab reference range will determine the threshold for normal vs. elevated status.

Summary tables with normal/elevated status for serum total IgE and LDH at baseline and each post-baseline visit (until end-of-study) will be provided by treatment group.

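### The SAP does not say whether scores after rescue are removed before the multiple-imputation model is fitted; read literally, they stay in

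*SAP*

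**What the plan says.** - **Protocol 9.5.2.2 (continuous endpoints).** Patients' "efficacy data through week 16 after the rescue treatment use will be set to missing". Worst observation carried forward (WOCF) then fills what is missing because of rescue, adverse event or lack of efficacy, and multiple imputation (MI) fills the rest.
- **SAP 5.6.2 (continuous endpoints).** "The WOCF approach will be used for data after rescue or missing due to withdrawn consent, AE, and lack of efficacy". Next, "The multiple imputation (MI) approach will be used for the missing due to other reasons, including reasons due to COVID-19". Then, on order: "The MI will be performed based on all observed data before the imputation by WOCF approach". The imputation model takes treatment, baseline, strata and the measured endpoint at every clinic visit. No rescue term is listed.
- **SAP 5.6, estimand table (key secondary endpoints).** "Initiation of rescue treatment: data after rescue treatment will be assigned by postbaseline" WOCF, labelled a hypothetical strategy. No step that first sets the data to missing is given.
- **SAP 5.6.1 (primary and co-primary binary endpoints).** For a Week 16 value missing for other reasons, "the data will be imputed using multiple imputation (MI) based on all observed values as described below". The underlying IGA or EASI score is imputed and response is derived from it. A rescued patient is a non-responder from rescue onward, but nothing says that the underlying scores leave the imputation data.
- **SAP 1.2.3 (changes from the Protocol).** The row on continuous responses still refers to Week 16 values missing because of rescue, and does not list the Protocol's set-to-missing rule as withdrawn.
- **SAP 4.3 and Protocol 5.3.** Rescued patients are asked to keep attending scheduled visits, so scores after rescue will exist.

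**The concern.** SAP 5.6.2 names data after rescue separately from missing data, fits the imputation model to observed data, and applies WOCF only afterwards. Followed to the letter, a rescued child's measured Week 8, 12 and 16 scores are in the dataset when the model is fitted, and are overwritten later. By then they have already shaped the regressions that impute Week 16 for children who were never rescued and are missing for other reasons, such as COVID-19.

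Two things are at stake. First, scores improved by rescue have no place in either declared strategy: composite for the binary endpoints, hypothetical for the continuous ones. Second, the SAP fixes 40 imputations and two seeds so that the result can be reproduced, yet leaves the input dataset open. Two programmers following the text could fit different models.

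**Working it through.** The plan gives no figure on this point, so there is none to reproduce. The check is a comparison of texts, followed by an illustration of size.

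**Order of operations**

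| Step | Protocol 9.5.2.2 | SAP 5.6.2, read literally |
|---|---|---|
| 1 | Remove values after rescue | (not stated) |
| 2 | WOCF for rescue, AE, lack of efficacy; MI for other reasons | Fit MI to all observed values |
| 3 | ANCOVA, combine | WOCF for data after rescue and for missing due to consent withdrawal, AE, lack of efficacy |
| 4 | | ANCOVA, combine |

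The Protocol's step 1 has no counterpart in SAP 5.6, 5.6.1 or 5.6.2, while SAP 1.2.3 speaks as if it had been done. For the binary endpoints the Protocol planned no MI (9.5.2.1: non-response after rescue or withdrawal). The SAP introduced it, so only the SAP can define its input.

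**Does wording elsewhere settle it?** SAP 5.11 lists two biomarker analyses. One uses "All observed data, regardless if rescue treatment is used or data is collected after study drug withdrawal"; the other uses observed data censored after rescue. The phrase is qualified both ways there, so its unqualified use in 5.6.2 has no default meaning.

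**Size.** The documents give no rescue rate, rescue effect or other-reason dropout rate. All of these inputs are assumptions.

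*Simulation 1.* 400 trials per setting, 80 per arm; rescue about 62% on placebo and 26% on dupilumab; rescue lowers EASI percent change by 15 to 30 points; 5 to 10% missing for other reasons. Keeping values after rescue makes imputed placebo values 7 to 14 points more favourable and moves the treatment difference 0.2 to 0.5 points toward zero, out of about 42.

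*Simulation 2.* 100,000 per arm; rescue 20 to 60% on placebo and 5 to 20% on dupilumab, likelier at higher EASI; rescue lowers EASI by 15 to 50%; 2 to 10% dropout among the un-rescued. Sequential regression on treatment, baseline and earlier visits was fitted with values after rescue removed, then kept. Rescued patients received pre-rescue WOCF in both. Settings with 10% dropout, mean EASI percent change:

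| Rescue dupilumab / placebo | Rescue effect | Placebo imputed: removed / kept | Dupilumab imputed: removed / kept | Difference: removed / kept | Shift |
|---|---|---|---|---|---|
| 5% / 20% | 30% | -23.8 / -27.1 | -67.1 / -67.1 | -48.10 / -47.83 | 0.27 |
| 10% / 40% | 50% | -28.9 / -38.4 | -67.5 / -67.9 | -49.31 / -48.78 | 0.53 |
| 20% / 60% | 50% | -32.8 / -44.9 | -68.4 / -70.0 | -48.50 / -48.15 | 0.35 |
| 20% / 60% | 15% | -33.8 / -35.1 | -69.1 / -69.8 | -48.45 / -48.45 | 0.00 |

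The shift is close to f_P × s_P − f_D × s_D, where f = (1 − rescue share) × dropout is the imputed fraction of an arm and s is the change in that arm's imputed mean:

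- Row 2: (0.60 × 0.10) × 9.5 − (0.90 × 0.10) × 0.4 = 0.570 − 0.036 = 0.53.
- Row 3: (0.40 × 0.10) × 12.1 − (0.80 × 0.10) × 1.6 = 0.484 − 0.128 = 0.36, against 0.35 simulated.

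A large change in the imputed values is thus diluted by the small fraction imputed. As a share of the effect, 0.53 / 49.31 = 1.1%, and in simulation 1, 0.5 / 42 = 1.2%. A separate check on EASI-75, also with assumed inputs, gave about 0.1 percentage points.

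**Limits.** These figures compare two inputs; they are not errors against a truth. In simulation 2 dropouts were drawn only from children never rescued. Against those placebo children's own rescue-free Week 16 values, removal came out 2.0 to 4.3 points too unfavourable. Keeping ranged from 2.6 points too unfavourable to 8.7 too favourable, and was the closer of the two at rescue effects of 15% and 30%. Simulation 2 examined means only and says nothing about standard errors or type I error.

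**The case against.** The strongest reply is that nothing has changed. SAP 1.2.3 exists to list departures from the Protocol, still treats Week 16 values after rescue as missing, and gives its reasons as clarifying WOCF and adding consent withdrawal. In 5.6.2 the sentence after the WOCF rule refers to the whole group, data after rescue included, as missing data. If those values are missing, they are not observed, and the sentence on order only keeps WOCF-filled values out of the MI model. That is a coherent reading and may be the intended one. It stands as far as showing that a departure is not established. It does not remove the conflict with the separate naming of data after rescue in 5.6.2, or with the estimand table.

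Two further points stand. The Protocol's set-to-missing rule is written for continuous endpoints, so it cannot be invoked for the binary ones. There, rescued children are non-responders either way, and the tipping-point analysis already stresses the imputed values. The effect on the treatment difference is also small.

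A reader might infer more: that the SAP has dropped the Protocol rule, that the contrast in 5.11 proves values after rescue are included, or that rescued trajectories dominate the imputed values. The documents support none of these. The rule is not listed as withdrawn; 5.11 uses the phrase both ways; and scores after rescue are only part of the data to which the model is fitted.

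**Conclusion.** The text is internally inconsistent on whether scores after rescue enter the MI model. Read literally, 5.6.1 and 5.6.2 include them; 1.2.3 implies that they are excluded. On the literal reading, and under the assumed rates, imputed placebo EASI percent change is about 1 to 14 points more favourable than under the Protocol's order (1 to 12 in one simulation, 7 to 14 in the other). The treatment difference moves by at most about 0.5 points, toward no effect.

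That direction depends on the assumption that rescue is commoner on placebo. The size grows with other-reason missingness and with the effect of rescue. A changed conclusion is unlikely, and the documents give no ground for saying that the wording favours dupilumab. The reason to act is that the imputation input is undefined for the primary, co-primary and key secondary analyses, and that including scores after rescue fits neither declared strategy. It is a minor point.

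**What to change.** Add to SAP 5.6.1 and 5.6.2, in substance:

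> Efficacy values after the first adjudicated rescue, including the underlying IGA and EASI scores, are set to missing before the MI model is fitted. Values after treatment discontinuation without rescue are retained (treatment policy). After MI, rescued patients are assigned non-response (binary endpoints) or WOCF taken from pre-rescue post-baseline visits (continuous endpoints), with the baseline value where there is none.

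For continuous endpoints this restores the Protocol's rule. For binary endpoints it defines the input to an imputation that the SAP itself introduced. If the sponsor does intend scores after rescue to inform the model, SAP 1.2.3 should list that as a change from the Protocol, with the reason.

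The cost is a few sentences and one filtering step in the imputation program, fixed before unblinding. It needs no new data and does not affect sample size or the testing order.
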